## Study protocol

This observational study evaluated the diagnostic and treatment-planning performance of three large language models (LLMs)—ChatGPT-4o, Claude 3.7 Sonnet, and Gemini Advanced—using real clinical cases collected from 120 patients who presented to an endodontic clinic. For each patient, a standardized case file was prepared that included demographic information, detailed medical and dental history, clinical findings (pain characteristics, percussion/palpation sensitivity, vitality testing, periodontal status, sinus tract presence, discoloration), and a periapical radiograph. All information was anonymized and presented in an identical, fixed order to all models.

Each LLM received the same single prompt (“Determine the diagnosis and propose the appropriate treatment plan”) and the same case structure. Radiographs were uploaded as original-resolution JPEG files through each platform’s native multimodal interface. Text was entered first, followed by the image upload. ChatGPT-4o, Gemini Advanced, and Claude 3.7 were all used in their default multimodal configurations with no web-browsing, plug-ins, external retrieval tools, OCR, or fine-tuning enabled. “Search with Gemini” was manually disabled.

Each case was submitted to the LLMs using newly created accounts, accessed via Google Chrome on a desktop computer. All questions were delivered within a 24-hour window and in the same predetermined order. No pre-testing, prompt engineering, or clarifying follow-up messages were allowed. If a model requested additional information, no further input was given. Each model generated only one response per case, reflecting real-world first-response performance.

To avoid contextual contamination, each case was entered in a separate chat session with cleared conversation history. All outputs were recorded verbatim and saved in Word format. A panel of

three independent endodontic specialists established the gold-standard diagnoses and treatment plans for all cases. Disagreements were resolved by consensus. AI responses were coded as “1” (consistent with gold standard) or “0” (inconsistent).

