Evaluating ChatGPT-4o, Gemini and Claude 3.7 in Endodontic Diagnostics:

A Prospective Clinical Study

NCT number: not applicable

Ethical Approval: Date: 26.06.2025, Protocol No: 2025-07-02/38

Record Release Date/Time: November 24, 2025 14:03

Last Updated: December 8, 2025

Statistical analysis

Data were entered into Excel and analyzed using SPSS (v27). Descriptive statistics were reported, and categorical comparisons were performed using Pearson chi-square or Fisher's Exact tests where appropriate, with a significance threshold of $p < 0.05$.

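### No masking of model identity is described for the 1/0 coding of free-text answers, the step on which the between-model comparison rests

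*Protocol*

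**What the plan says.** All of the relevant text is in the Protocol, under Study protocol.

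- The material is "real clinical cases collected from 120 patients who presented to an endodontic clinic", each case being put to three models. On repetition: "Each model generated only one response per case, reflecting real-world first-response performance". That makes 120 × 3 = 360 responses.
- The prompt is open and asks for both a diagnosis and a treatment plan. On storage: "All outputs were recorded verbatim and saved in Word format".
- On the reference: "three independent endodontic specialists established the gold-standard diagnoses and treatment plans for all cases", followed by "Disagreements were resolved by consensus".
- On the outcome: "AI responses were coded as “1” (consistent with gold standard) or “0” (inconsistent".

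The SAP, under Statistical analysis, covers software, descriptive statistics, tests and the significance threshold. On the comparison it says "categorical comparisons were performed using Pearson chi-square or Fisher's Exact tests where appropriate". It does not mention coding.

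**The concern.** Deciding whether a verbatim free-text answer agrees with a reference diagnosis and plan takes human judgement, most of all when the answer is partial, offers several options or is worded differently. If the coder knows which model wrote the answer, doubtful answers can be resolved more generously for one model than for another.

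The 1/0 code is the only performance measure described, so one-sided generosity passes straight into the accuracies and their order. No later analysis can recover from it. The planned tests take the codes as given, and so would a test matched on case.

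The protocol controls tightly what the models receive (prompt, order, accounts, sessions, no follow-up). It describes no comparable control on how their answers become data.

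**Working it through.** **1. Does any wording already supply the safeguard?**

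- "All information was anonymized and presented in an identical, fixed order to all models" concerns the case files given to the models, not the outputs given to the coder.
- The independence and the consensus belong to the panel that set the reference. No duplicate coding of responses is described.
- Verbatim storage preserves the outputs and makes recoding possible, but it does not conceal their source.
- The SAP is silent.

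So neither masking nor shuffling at coding is described. The coder's role and a rule for partial, multiple-option or reworded answers are also absent. Those two are reporting gaps that could affect all models alike, and the figures below do not size them.

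**2. Shift in accuracy.** The documents state no accuracy, effect size or power, so there is no figure of the plan to reproduce. The only input from the documents is n = 120 cases per model. With net leniency of k cases towards one model, shift = k/120. The share of that model's wrong answers that must be accepted is k / [120 × (1 − p)], where p is its true accuracy (assumed 50–80%). For example, with k = 6 and p = 0.80: 6 / (120 × 0.20) = 6/24 = 25%.

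| k | Shift (points) | Share of errors accepted at p = 50 / 60 / 70 / 80% |
|---|---|---|
| 3 | 2.5 | 5.0 / 6.3 / 8.3 / 12.5% |
| 6 | 5.0 | 10.0 / 12.5 / 16.7 / 25.0% |
| 12 | 10.0 | 20.0 / 25.0 / 33.3 / 50.0% |

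The text does not say whether a response receives one code or separate codes for diagnosis and treatment. The arithmetic applies to any single 1/0 outcome in either case.

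**3. Effect on ranking and tests when the models are truly equal.** Simulation with all inputs but n assumed: three models answer the same 120 cases; true accuracy is equal at 50, 60, 70 or 80%; within-case correlation is 0.2, 0.4 or 0.6. Each wrong answer of one model is accepted with probability (k/120)/(1 − p), so k is the expected number. There are 40,000 replicates per setting. The test is the 3×2 Pearson chi-square with critical value 5.991. Ranges are over all settings.

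| k | Favoured model ranks first (ties split) | Planned chi-square rejects | Cochran's Q (matched) rejects |
|---|---|---|---|
| 0 | 33–34% | 0–2.5% | 4.8–5.2% |
| 3 | 52–65% | 0.3–4% | – |
| 6 | 69–88% | 2–12% | 13–31% |
| 12 | – | 23–57% | – |

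The last column shows that matching on case does not remove the bias.

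**4. Effect on ranking when another model is truly better.** One other model is better by the stated gap and the third equals the favoured one. Favoured accuracy is 50% or 70%, correlation 0.2–0.6, with 20,000 replicates (all assumed). Entries are how often the favoured model ranks first.

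| True gap | k = 0 | k = 3 | k = 6 |
|---|---|---|---|
| 5 points | – | 25–29% | 46–48% |
| 10 points | about 1–4% | about 4–9% | about 12–19% |
| 15 points | – | at most about 2% | at most about 4% |

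**5. Why small leniency seldom yields significance.** If the other two models have identical counts, the extra 1 codes needed for p < 0.05 in the 3×2 test number 17, 16, 15 and 13 at 50, 60, 70 and 80% agreement. All exceed 12.

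**The case against.** The strongest reply is that this is a reporting gap. The protocol text is a short summary in the past tense, silence does not show how coding was done, and no document supports leniency of any size or direction. That stands as far as it goes. A reader might infer that the coder saw the model names; the documents do not say so. But the written procedure, followed exactly, leaves the coding step open, and a better procedure costs little. The point therefore goes beyond a missing detail.

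A reader might also infer that the study has no protection against bias at all. That is too strong. Three specialists with consensus protect the reference standard, and verbatim storage makes the coding open to audit. What is unprotected, as described, is the step from answer to code.

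A third inference is that the gold standard was shaped by the outputs, since its timing is not stated. One standard per case serves all three models, so timing can favour a model only if the panel saw outputs first, and nothing says that it did. This is secondary.

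Finally, exact equality is the setting in which ranking is most fragile. That objection stands. With a true gap of 10 or 15 points the distortion is much smaller, though at 5 points it remains material.

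**Conclusion.** The concern holds in limited form: no masking or shuffling is described at the coding step, and none of the controls that are described acts there. Whether coding was in fact unmasked cannot be told from the documents.

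The size is unknown. On the stated assumptions, leniency of 3 to 6 cases mainly distorts a model's estimated accuracy (2.5 to 5 points) and the ranking of models that are close. It should not be read as a large inflation of false positives. With equal models and within-case correlation of 0.2–0.6, chi-square rejection stays at or below about 12% up to 6 cases. Rates of 23–57% need 12 cases, which at 80% accuracy is half of one model's errors. The accuracies, correlations, gaps and leniency levels are all assumptions; only the 120 cases and three models come from the documents.

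This should be addressed as a low-cost improvement. Confidence is medium.

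**What to change.** Specify the coding as follows:

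1. Lock the consensus gold standard, together with a written matching rule for partial, multiple-option and differently worded answers.
2. Strip model names and self-identifying text from the 360 saved outputs.
3. Shuffle the three answers within each case under random codes.
4. Have an existing team member code them masked to model.

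State also whether diagnosis and treatment are coded together or separately.

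*If coding was already masked:* say so, give the coder's role, and say when the gold standard was fixed. The cost is one or two sentences.

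*If it was not:* recode masked from the saved Word files, report both sets of codes with their agreement, base the between-model comparison on the masked codes, and disclose the change as post hoc. The cost is modest file preparation and one coding pass over 360 outputs, with no new patients or model runs.

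Downsides: masking is imperfect because style or memory may reveal the model, and a recoder from the team may already know the results. Replacing codes also changes outcome data after the fact, which is why both sets must be shown.

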Evaluating ChatGPT-4o, Gemini and Claude 3.7 in Endodontic Diagnostics:

A Prospective Clinical Study

NCT number: not applicable

Ethical Approval: Date: 26.06.2025, Protocol No: 2025-07-02/38

Record Release Date/Time: November 24, 2025 14:03

Last Updated: December 8, 2025

Statistical analysis

Data were entered into Excel and analyzed using SPSS (v27). Descriptive statistics were reported, and categorical comparisons were performed using Pearson chi-square or Fisher's Exact tests where appropriate, with a significance threshold of $p < 0.05$.

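### Must the plan specify agreement by diagnosis and treatment category, beside overall agreement?

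*SAP*

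**What the plan says.** The Protocol (Study protocol) states that the study "evaluated the diagnostic and treatment-planning performance of three large language models", "using real clinical cases collected from 120 patients who presented to an endodontic clinic". The reference standard is a panel: "three independent endodontic specialists established the gold-standard diagnoses and treatment plans for all cases". Scoring is binary, with 1 for a response that matches the panel and 0 for one that does not. The kind of wrong answer is not coded, but the raw text is kept: "All outputs were recorded verbatim and saved in Word format". The Protocol also says what the score is meant to represent: "Each model generated only one response per case, reflecting real-world first-response performance".

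The SAP (Statistical analysis) is brief: "Descriptive statistics were reported, and categorical comparisons were performed using Pearson chi-square" or Fisher's exact tests, with a 0.05 threshold. It does not say which descriptive statistics. Neither document lists diagnosis or treatment categories, gives the case mix, or mentions agreement by category, a commonest-answer benchmark or a cross-tabulation of answers.

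**The concern.** Diagnosis means telling conditions apart. Overall agreement is the case-mix-weighted average of agreement in each category, so the same total can come from quite different performance in the less common conditions. Cases came from patients attending a clinic and no balancing by diagnosis is described, so one category could dominate. A high percentage might then partly reflect how often the common answer happens to be right, and a test on the totals could not separate such a model from one that distinguishes conditions. A reader might also take the overall figure as the accuracy to expect in a rarer condition. If this were a true defect, the study's main result would not answer its stated aim.

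**Working it through.** **Inputs.** From the Protocol: 120 cases; three models; one response per model per case, hence 120 responses per model and 120 × 3 = 360 in all; a 1/0 code. The documents give no case mix, category list, expected agreement or sample-size calculation, so there is no stated figure to reproduce. The commonest category's share, m, is assumed at 25%, 50%, 70% and 80%. (As the commonest share, 25% needs at least four categories.)

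**1. Score of a constant answer.** Always giving the commonest category scores 120m: 30, 60, 84 and 96 of 120.

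**2. What an overall score allows in the other categories.** With X correct in total, 120m common cases and n = 120 − 120m others, agreement in the others, pooled, lies between max(0, X − 120m)/n and min(n, X)/n.

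| Overall | m = 25% (n = 90) | m = 50% (n = 60) | m = 70% (n = 36) | m = 80% (n = 24) |
|---|---|---|---|---|
| 84/120 (70%) | 60–93% | 40–100% | 0–100% | 0–100% |
| 96/120 (80%) | 73–100% | 60–100% | 33–100% | 0–100% |
| 108/120 (90%) | 87–100% | 80–100% | 67–100% | 50–100% |

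For example, 96/120 at m = 70% gives a lower bound of (96 − 84)/36 = 12/36 = 33%. These are worst-case limits, not forecasts. They narrow as m falls or overall agreement rises.

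**3. Two models with one score.** At m = 70%, 84/84 + 0/36 and 59/84 + 25/36 both total 84/120, and a Pearson test on the totals gives p = 1. The arithmetic behind the concern is correct.

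**4. What the gap between overall and other-category agreement measures.** Let a be agreement in common cases and b in the others. Overall agreement is ma + (1 − m)b, so overall minus b is m(a − b). For 80% and 50% this is 0.30m: 7.5, 15, 21 and 24 points across the four values of m. It is zero when a = b. It therefore measures uneven accuracy, which can arise because rarer conditions are harder as well as because a model favours the common answer.

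**5. Whether agreement by category would show a lean.** Take m = 50%, a = 80%, b = 50%: 48/60 common and 30/60 other cases right, 78/120 overall. Suppose all 30 errors in the other cases were the common answer. The model then gave the common answer 48 + 30 = 78 times against 60 true cases. Suppose instead all 30 were other wrong answers, which needs at least three categories. It then gave the common answer 48 times. The 1/0 data by category are identical in both. Short of extremes such as 0/36, only re-coding the 360 saved responses by the category actually given would tell the two apart.

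**6. Precision.** Wilson 95% intervals: 8/12, 39–86%; 16/24, 47–82%; 25/36, 53–82%; against 84/120, 61–77%.

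**The case for a change.** The best case for a change runs as follows. The aim is diagnostic performance, and without the case mix a reader cannot tell whether 70% is good or is what the commonest answer alone would score. The effect does not need an extreme mix: at m = 50%, an overall 80% still allows 60% to 100% in the other cases. Naming descriptive statistics commits the authors to nothing, so a reader cannot tell a planned breakdown from one chosen after the results were seen. The panel's labels exist and the responses were saved, so no new data are needed.

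Much of this stands. The commitment is absent, and a case-mix table with agreement by category would help interpretation. It remains a point about reporting detail. It does not show that the stated summary is wrong for what it estimates, and the size of the problem depends on a mix that the documents do not give. The cheap tables answer only whether accuracy varies by category. The question of leaning needs all 360 responses re-read. Even the cheap tables presuppose that each panel diagnosis and treatment plan fits a single category, which the Protocol does not say; and if one code covers diagnosis and treatment together, the responses would first have to be scored for each. A model that answers every case alike is a useful reference point, but nothing in the Protocol suggests it: each case had its own findings and radiograph and was entered in a separate session.

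**Conclusion.** No change to the plan is needed. The omission is real, but it is a gap in detail that analysts can fill sensibly under the existing wording. Overall agreement is a valid accuracy estimate for these 120 cases and fits the first-response aim, and all three models faced the same case mix. Following the plan on this point gives no wrong result.

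The size of the interpretive issue ranges from small to large with the assumed mix. An overall 90% with a 25% commonest share leaves 87% to 100% for the other cases; an overall 70% with a 70% or 80% share leaves 0% to 100%. That supports caution in reading the overall percentage, which should not be taken as accuracy in each condition. A breakdown, if the authors give one, is descriptive and will be imprecise in rare categories. It should not be presented as evidence that a model leans towards common answers unless the saved responses have been re-coded and cross-tabulated against the panel's categories. This conclusion concerns the choice of summary only. It takes no position on which test suits three models scored on the same cases.

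### The SAP plans no interval for any model's accuracy or for any between-model difference, and its independent-sample tests ignore that all three models answer the same 120 cases

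*SAP*

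**What the plan says.** The Statistical analysis section of the SAP has two sentences. The first names the software. The second reads "Descriptive statistics were reported, and categorical comparisons were performed using Pearson chi-square", adds Fisher's exact test where appropriate, and sets significance at p < 0.05. It names no confidence interval, no estimate of a difference and no matched method.

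The Protocol (Study protocol) says that the study "evaluated the diagnostic and treatment-planning performance of three large language models", "using real clinical cases collected from 120 patients who presented to an endodontic clinic". The design is fully crossed. On the input side, "All information was anonymized and presented in an identical, fixed order to all models"; on the output side, "Each model generated only one response per case". A specialist panel "established the gold-standard diagnoses and treatment plans for all cases", and each response is coded 1 or 0 against that standard.

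Neither document gives expected accuracies, a power or precision basis for 120 cases, a margin, or a rule for reading a non-significant result.

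**The concern.** Evaluating performance is an estimation question: how often is each model right, and how far apart are the models? A p-value answers neither. Followed as written, the plan delivers unspecified descriptive statistics and a significant or non-significant label.

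The second problem is the design. Because each case is answered by all three models, the 0/1 codes are matched by case. Pearson and Fisher tests treat the models' results as independent samples, so the information on which cases the models split on is not used. That information sets the width of the interval for a difference, and readers cannot recover it from published percentages.

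What is at stake is the strength of the conclusions about differences. The same pair of percentages can exclude a zero gap or not, depending on the matched pattern, and the plan would show neither that nor the range of gaps still compatible with the data.

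**Working it through.** **Inputs.** From the Protocol: n = 120 cases, three models (three pairwise differences), one binary result per model per case. From the SAP: threshold 0.05, taken here as two-sided because sidedness is not stated. Assumed, because the documents give no values: accuracies of 50% to 90%, and a discordant share of 20% to 40%, meaning the proportion of cases on which exactly one of two models is right. The figure 120 comes with no calculation, so there is nothing to reproduce.

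**1. Precision of one accuracy.** Wilson interval: [p + z²/2n ± z√(p(1-p)/n + z²/4n²)] / (1 + z²/n), with z = 1.96 and n = 120.

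| Correct | Accuracy | 95% interval |
|---|---|---|
| 60/120 | 50% | 41.2 to 58.8 |
| 84/120 | 70% | 61.3 to 77.5 |
| 96/120 | 80% | 72.0 to 86.2 |
| 108/120 | 90% | 83.3 to 94.2 |

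The half-width is about ±9 points at 50% and about ±5 at 90%.

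**2. One assumed pair, 84/120 against 96/120, by the test the SAP names.** The pooled proportion is 180/240 = 0.75, so the standard error is √(2 × 0.75 × 0.25/120) = 0.0559. Then z = 0.10/0.0559 = 1.79 and p = 0.074. The corresponding unmatched interval is 10 ± 1.96√((0.70 × 0.30 + 0.80 × 0.20)/120) × 100, or -0.9 to +20.9 points.

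**3. The same pair, using the matching.** The difference is 12 cases, d = 0.10. With discordant share ψ there are m = 120ψ discordant cases. McNemar (uncorrected) is z = 12/√m. The matched Wald interval is d ± 1.96√((ψ - d²)/120).

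| ψ | m | McNemar z | p | Matched 95% interval (points) |
|---|---|---|---|---|
| 20% | 24 | 2.45 | 0.014 | 2.2 to 17.8 |
| 30% | 36 | 2.00 | 0.046 | 0.4 to 19.6 |
| 40% | 48 | 1.73 | 0.083 | -1.2 to 21.2 |

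If the two models' errors were unrelated, ψ would be 0.70 × 0.20 + 0.30 × 0.80 = 38%. The first two rows therefore describe models that tend to fail on the same cases. These are Wald intervals, used because they can be checked by hand; score intervals will differ somewhat.

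**4. What an observed gap near zero leaves open.** The matched half-width is 1.96√(ψ/120): 8.0 points at ψ = 20%, 9.8 at 30% and 11.3 at 40%. A 10-point gap is thus excluded in the first two cases but not in the third. The observed gap matters too. At ψ = 20%, an observed gap of 8 cases (6.7 points) gives z = 8/√24 = 1.63, which is non-significant, with an upper limit of 6.7 + 1.96√((0.20 - 0.0044)/120) × 100 = 14.6 points. Accuracy matters in the unmatched calculation: 1.96√(2p(1-p)/120) is ±12.7 points at 50%, ±11.6 at 70% and ±7.6 at 90%.

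**The case against.** Three stronger readings are tempting, and the documents do not support them.

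- A reader might infer that a non-significant result is meant to be reported as equal performance. Neither document states an aim, margin or claim of equality, similarity or non-inferiority, and the SAP does not say how p >= 0.05 will be read. Silence is not a planned equivalence claim.
- A reader might infer that any null result on 120 cases leaves gaps above 10 points plausible. Step 4 shows that this depends on discordance, accuracy and the observed gap. Ten points is also not a threshold found in the documents.
- A reader might calculate two-sample power at 120 per model and conclude that the study is too small. Such a figure treats the models as independent, so part of any shortfall comes from ignoring the matching. Adding intervals would not change power in any case.

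Other objections carry some weight. The SAP does not say that comparisons are pairwise; a single three-by-two table fits its wording equally well, and then p = 0.074 would not be the reported result. Descriptive statistics could be taken to include intervals, although none is named and the term does not ordinarily cover an interval for a difference. Anyone can compute a single-model interval from a percentage and n = 120, so that omission does limited harm. The interval for a between-model difference is another matter: it needs the matched codes, which only the study team holds. That part of the concern stands in full.

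**Conclusion.** The concern holds as a choice of analysis that should be improved. The plan offers only descriptive statistics and independent-sample p-values for a study that asks about performance and is matched by case. As written, it cannot state how large a between-model gap the data support or rule out.

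The size is conditional on assumed values. For 84/120 against 96/120, the named test is non-significant at p = 0.074, while the matched interval excludes zero at 20% and 30% discordance and includes it at 40%. Near a zero gap, the matched half-width runs from about 8 to 11 points over the same range. None of this shows that the study's conclusions are wrong. It shows that the plan leaves out the quantities needed to judge them.

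**What to change.** Keep the existing sentence for descriptive statistics and the 0.05 threshold. Add the following to the SAP, separately for diagnosis and for treatment plan:

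1. Each model's accuracy is reported with a Wilson 95% confidence interval. At 120 cases this is about ±5 points at 90% accuracy and ±9 at 50%.
2. Each of the three pairwise differences is reported in percentage points with a 95% score interval for matched proportions (for example Tango or Newcombe), computed from the case-matched 0/1 codes. Any accompanying p-value comes from a matched test: McNemar for pairs, Cochran's Q overall. State whether the three intervals are adjusted for multiplicity.
3. Conclusions about differences rest on these intervals. A p-value of 0.05 or more is not, on its own, described as equal or comparable performance.

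The cost is SAP wording and slightly more output, with no new patients or prompts. Results will look less certain than bare percentages. One point to check: the Protocol does not say whether diagnosis and treatment plan were coded separately. If only one combined code was kept, the responses, which the Protocol says were saved verbatim, would need to be recoded against the panel's two standards.

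### The SAP names only independent-samples tests, but all three models answered the same 120 cases, so the between-model comparison should use a matched analysis

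*SAP*

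**What the plan says.** The Statistical analysis section of the SAP states that "categorical comparisons were performed using Pearson chi-square or Fisher's Exact tests where appropriate", with a 5% threshold. It does not list the comparisons, and it names no other test.

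The Study protocol section of the Protocol describes a fully crossed design. The material is "real clinical cases collected from 120 patients who presented to an endodontic clinic". On presentation it says "All information was anonymized and presented in an identical, fixed order to all models", and on replication "Each model generated only one response per case". A panel of "three independent endodontic specialists established the gold-standard diagnoses and treatment plans for all cases", and each response was scored 1 or 0 for agreement with that reference.

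Neither document mentions Cochran's Q, McNemar's test, GEE, a mixed model or any other allowance for matching. Neither gives an expected accuracy, a within-case correlation or a power calculation.

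**The concern.** Each case is a block of three scores, one per model. All three models see the same file and radiograph and are judged against the same panel decision. An easy or ambiguous case may therefore move all three scores together.

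Pearson and Fisher tests treat the 3 × 120 = 360 scores as independent. They hold their stated level only if the models' scores are uncorrelated within a case. With positive correlation they overstate the variance of the between-model differences, so real differences can be missed. With negative correlation the error goes the other way and the test rejects too often.

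The SAP does not say that these tests are for the between-model comparison; that is an inference. Comparing the three models is the evident main aim, however, and no other test is offered for it.

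**Working it through.** **Inputs.** From the Protocol: n = 120 cases, k = 3 models, one binary score per model per case. From the SAP: Pearson or Fisher, alpha 0.05. Assumed, because the documents do not give them: the within-case correlation rho (taken as equal for each pair of models) and the accuracies. The plan has no figure of its own to reproduce.

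**1. True size of the three-model Pearson test.** If the models are equally accurate, the Pearson statistic is distributed approximately as (1 − rho) × chi-square on 2 df. For 2 df the tail probability is exp(−x/2), so size = 0.05^(1/(1 − rho)). At rho = 0.3, for example, 0.05^(1/0.7) = 0.014. The simulated column uses n = 120, accuracy 75% and 20,000 replicates.

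| rho | Formula | Simulated |
|---|---|---|
| −0.1 | 6.6% | 6.5% |
| 0 | 5.0% | 5.1% |
| 0.1 | 3.6% | 3.5% |
| 0.2 | 2.4% | 2.4% |
| 0.3 | 1.4% | 1.4% |
| 0.5 | 0.25% | 0.2% |

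Cochran's Q stayed between 4.9% and 5.3% in the same simulations.

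**2. Power.** Assumed accuracies 70, 75 and 82%; n = 120; correlated latent normals calibrated so that each pair of 0/1 scores has correlation rho; 60,000 replicates. A different latent structure moves the results by 1 to 2 points.

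| rho | Pearson | Cochran's Q |
|---|---|---|
| 0 | 48% | 48% |
| 0.1 | 47% | 53% |
| 0.2 | 46% | 58% |
| 0.3 | 45% | 65% |
| 0.5 | 41% | 81% |

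A separate calculation with accuracies of 65, 70 and 80% shows the same pattern: 66% v 66% at rho = 0, and 66% v 82% at rho of about 0.31.

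**3. Worked example.** Assume 84, 90 and 98 correct of 120.

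- Mean = 272/3 = 90.67. Sum of squared deviations SS = 44.44 + 0.44 + 53.78 = 98.67 (unrounded).
- Pooled accuracy = 272/360 = 0.7556. Pearson = SS/(120 × 0.7556 × 0.2444) = 4.45 on 2 df, p = 0.108, however the models' errors overlap.
- Let D be the number of cases on which the three models do not all agree. For k = 3, Q = 3 × SS/D = 296/D.
- Link between D and rho: each such case contributes two discordant pairs of models. Hence D = 60 × [sum over pairs of (p_j q_k + p_k q_j) − 2 × rho × sum over pairs of s_j s_k], where q = 1 − p and s = √(pq). Here that is D = 66.9 − 65.2 × rho.

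| D | rho (approx.) | Q | p |
|---|---|---|---|
| 67 | 0 | 4.42 | 0.110 |
| 60 | 0.11 | 4.93 | 0.085 |
| 47 | 0.31 | 6.30 | 0.043 |
| 34 | 0.50 | 8.71 | 0.013 |

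Q exceeds 5.991 when D is 49 or less (296/49 = 6.04), that is, when rho is about 0.27 or more.

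**4. Pairwise follow-up in the same example.** In one layout with D = 47, the 84 v 98 pair has 9 v 23 discordant cases. Exact McNemar p = 0.020. The paired difference is (23 − 9)/120 = 11.7 points, with standard error √(32 − 14²/120)/120 = 4.6 points and 95% CI 2.7 to 20.7. This passes behind a significant Q (p = 0.043), but under Holm alone it becomes 3 × 0.020 = 0.060. In a layout with D = 34 and 5 v 19 discordant cases, p = 0.0066 and Holm gives 0.020. The multiplicity rule therefore has to be stated.

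**The case against.** The strongest reply accepts the mismatch and disputes how much it matters.

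- **The harm is conditional.** It is a possible false negative that depends on an undocumented correlation. The loss is nil at rho = 0 and small at 0.1, and a significant result is not undermined by positive correlation. All of this stands. It does not rescue the test, because Cochran's Q needs no knowledge of rho and has the same power as Pearson at rho = 0.
- **The accuracies chosen show the problem at its clearest.** This stands as a limit. With assumed accuracies of 60, 75 and 85%, Pearson v Q power is 98.9% v 99.3% at rho = 0.1 and 99.5% v 99.9% at 0.3, so almost nothing is lost. With 72, 75 and 78% both tests are weak, about 8% v 18% at rho = 0.3. A large loss from about rho = 0.3 applies to small or intermediate differences only.
- **The SAP may intend these tests for patient-group comparisons within one model.** That is possible, but the main comparison would then have no test at all, and the SAP would still need changing. The SAP's qualifier about appropriateness chooses only between two independent-samples tests.
- **Separate codes for diagnosis and treatment plan are not stated outright.** The Protocol names both tasks and a reference standard for each, so separate codes are the natural reading. They should still be confirmed.

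**Conclusion.** The concern holds, and the analysis must be changed. The only tests in the plan ignore the matching that the Protocol's design creates.

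Under positive within-case correlation, the three-model Pearson test runs at about 3.6% (rho = 0.1) down to 0.25% (rho = 0.5) instead of 5%. For intermediate differences such as 70, 75 and 82%, it gives up about 6 power points at rho = 0.1 (53 − 47), 20 at 0.3 (65 − 45) and 40 at 0.5 (81 − 41) against Cochran's Q. The exposed conclusion is a non-significant one.

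These sizes rest on assumed correlations and accuracies. Positive correlation is plausible but undocumented; a negative value would instead push the error rate above 5% (6.6% at rho = −0.1). That the scores are matched, and that the named tests ignore this, rests on no such assumption.

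**What to change.** For between-model comparisons, replace Pearson/Fisher with Cochran's Q on the 120 matched cases, separately for diagnosis and for treatment plan. If Q is significant, follow with pairwise exact McNemar tests under a stated rule: either the Q gate, which suffices for three models within one outcome, or Holm. Also state how the two outcomes are handled together, since the Q gate does not cover that. Report the discordant counts and the paired accuracy differences with 95% CIs.

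A logistic GEE clustered on case is an acceptable alternative, though it gives odds ratios and a Wald-type test. Keep Pearson/Fisher only for comparisons between different patients.

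The cost is a few sentences in the SAP and a re-run on the existing 0/1 codes, with no new data collection. First confirm that the codes are linked by case and that diagnosis and treatment plan were coded separately. If only one combined code exists, the saved outputs would have to be re-scored to analyse the two outcomes separately. The SAP is written in the past tense, so disclose the re-run as a change to the analysis.
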